Does the protocol involve the handling and labeling of biological samples? If applicable, mention the procedures that will be used

Yes, with the patient's initials, date of birth, internal laboratory patient number, and randomization number.

Information to ensure that obtained biological samples will not be used for permanent or immortal cell lines or purposes unrelated to the study

Qualified personnel will take samples for this activity and will be processed within the institution. Samples will not be sent to any other institution/company, so there is no risk of being used for purposes other than those stipulated in the protocol.

Description of treatment groups

Included subjects will be randomized 1:1 to receive:

- **Group 1:** Dapagliflozin 10 mg/day + Metformin 2000 mg/day and, if necessary, as mentioned previously, rescue treatment.
- **Group 2:** Metformin 2000 mg/day and, if necessary, as mentioned previously, rescue treatment. Treatments will be administered for 12 weeks. Patients who do not tolerate Metformin at a dose of 2000 mg will have their dose adjusted to 1500 mg daily. If patients do not tolerate 1500 mg daily, the dose will be titrated to 1000 mg daily. If they do not tolerate this dose, they will be withdrawn from the study.

Mechanisms for treatment assignment

The <https://www.google.com/search?q=randomization.com> tool will be used (The Table is attached as Appendix 1 of the protocol).

If a placebo group is used, include its justification

Not applicable

Criteria for premature withdrawal from the study

- Allergic reaction to any of the study medications or their excipients.
- Patients who do not tolerate Metformin 1000 mg/day.
- Severe life-threatening illness.
- Pregnancy during the study.
- Presence of acute renal failure (decrease in > 40% of glomerular filtration rate).
- Lactic acidosis or ketoacidosis.

Procedures for withdrawing a patient from the study

The patient will be notified of withdrawal from the protocol and will receive standard treatment, according to AACE 2019 guidelines (MET, GLP1 agonist, SGLT2 inhibitor, DPP4i, acarbose, thiazolidinediones, insulin, or sulfonylurea) and will be referred for follow-up at the secondary care level.

Criteria for premature (partial or complete) suspension of the study

NA

Selection Criteria

a) Inclusion criteria

- Subjects > 18-77 years old.
- Both men and women.
- HbA1c \geq 7.7% <12% (HbA1c from 9 to <12%: without catabolic symptoms).
- BMI $>$ 25 kg/m².
- Diagnosis of T2D: if a patient has taken any drug and/or insulin, they will be prescribed only Metformin as a washout period in the pre-randomization phase for 2 weeks.

b) Exclusion criteria

- Complications related to T2D and catabolic symptoms.
- HbA1c $>$ 9% with catabolic symptoms.

- CKD-EPI creatinine clearance: <60 ml/min.
- LADA or T1D.
- Concomitant clinically significant disease such as: liver, hematological, oncological, psychiatric, or rheumatic disease.
- Symptoms of markedly uncontrolled diabetes: (marked polyuria or polydipsia + 10% weight loss within the last 3 months before enrollment).
- Known hypersensitivity to dapagliflozin, metformin, or any of the drug excipients.
- Unstable or rapidly progressing kidney disease.
- Patients with severe liver failure (Child-Pugh class C).
- Patients with bariatric surgery.
- Any major CV event / vascular disease within 3 months before signing consent at enrollment, as assessed by the investigator.
- For women only: currently pregnant (confirmed with a positive pregnancy test) or lactating.
- Being hospitalized or having less than one month since hospital discharge.

c) Elimination criteria

- Allergy to dapagliflozin, severe life-threatening illness, or pregnancy during the study.
- Patients presenting with acute renal failure (decrease in > 40% of GFR)
- For women only: pregnancy confirmed with serum chorionic gonadotropin. In case of pregnancy during the study, the subject must be eliminated from the trial, offered standard treatment indicated in point 36, and the Pregnancy Outcome Report (Annex) must be completed to record essential details of the mother. Part I should be completed after pregnancy identification and Part II is to record the pregnancy outcome.

39. Outcomes and Variables

- **Primary Variable:** Change from baseline in GV (MAGE) in mg/dL after 12 weeks of treatment between the DAPA+ MET group versus the MET monotherapy group.
- **Secondary Variables:**
 - Change from baseline (absolute difference) in HbA1c levels (%) after 12 weeks of treatment between the DAPA + MET group versus the MET monotherapy group.
 - Change from baseline (total difference) in insulin levels (μ U/mL) after 12 weeks of treatment between the DAPA + MET group versus the MET monotherapy group.
 - Change from baseline (absolute difference) in oxidative stress measurement (total antioxidant capacity) after 12 weeks of treatment between the DAPA + MET group versus the MET monotherapy group.

- Change from baseline (total difference) in the measurement of inflammation biomarkers (VCAM-1 and adiponectin) after 12 weeks of treatment between the DAPA + MET group versus the MET monotherapy group.
- Change from baseline (absolute difference) in body fat quantification after 12 weeks of treatment between the DAPA + MET group versus the MET monotherapy group.
- Change from baseline (total difference) in the parameters of cardio-metabolic risk factors (weight (kg), total cholesterol (mg/dL), HDL (mg/dL), LDLc (mg/dL), albuminuria (mg/mg creatinine), and blood pressure (mmHg)) after 12 weeks of treatment between the DAPA + MET group versus the MET monotherapy group.

Methods to be used to contact patients

Personal contact data such as landline and mobile phone numbers, email address will be obtained via Phone call/Videocall, Whatsapp, Teams, Zoom, or Google Forms. Due to the SARS-CoV-2 pandemic, investigators will conduct home visits and/or collect data and hold medical consultations via Phone call/Videocall, Whatsapp, Teams, Zoom, or Google Forms.

Statistical Analysis (Description of the information processing and presentation plan. Include justification for the statistical tests to be used)

Stratified randomization in both groups to balance patient types and control potential bias. The normality of variables will be analyzed using the Kolmogorov-Smirnov test. According to the distribution of variables, they will be expressed as mean and standard deviation (SD) or median and interquartile range (IQR) for normally or skewed distributed variables, respectively. GV will be determined using the MAGE index. Comparison between the two groups will be evaluated using ANCOVA. A p-value based on two-tailed tests ≤ 0.05 will be considered significant. All analyses will be performed with SPSS 20.0 (Chicago, IL). Patients experiencing an acute stress event during the study will be excluded from the analysis due to the impact on GV.

Justification of sample size (include study power and the p-value considered significant)

The sample size was determined using the difference of means formula:

$$n = (Z\alpha / 2 + Z\beta)^2 * 2 * \sigma^2 / d^2,$$

A reduction in glucose variability from 4.85 to 2.2 was estimated with an expected standard deviation of 2.8 in the MAGE index, with an alpha value of 0.05 and a power of 0.80, resulting in a sample size of 88 subjects, with 44 subjects in each treatment group. No adjustments were included in the sample size calculation to estimate the number of subjects required for the

estimated differences in secondary variables.

Recruitment potential (number of subjects intended to recruit)

It is estimated that approximately 15% of the subjects who start the project and enter the pre-randomization period will not meet the criteria for the treatment period. Therefore, it is estimated that approximately 102 subjects will be assessed.

If multicenter, include the global and local sample number

Not applicable

Procedures for reporting deviations from the original statistical plan

A letter will be sent to the research committee for approval.

Possible discomforts resulting from the study

Frequency of follow-up visits, blood sample collection.

Potential risks

Those inherent to blood sampling.

Methods for detecting anticipated risks

Patients will be asked to report any side effects 24 hours a day. Patients will be able to contact the participating medical staff at any time.

Safety measures for timely diagnosis and prevention of risks

Patients reporting a side effect will be scheduled for evaluation.

Procedures to follow to resolve risks if they occur

Depending on the case, treatment for the complication or side effect will be provided, either with an outpatient prescription or the patient will be referred to the emergency department for assessment and treatment. Medical expense insurance will be available to cover treatment costs for patients associated with adverse effects secondary to the use of study medications.

Expected direct benefits

Patients who agree to participate in this research study will be comprehensively evaluated and more frequently compared to the standard treatment (see point 36) available at the time, giving the patient an advantage in better managing their disease. The additional tests performed could improve glucose control and also evaluate the function of other organs and systems. The medications administered during the study will lower blood glucose, thus, it is expected that microvascular complications will be prevented. Improvement in GV and control of plasma glucose levels will reduce the short-term risks associated with hypoglycemic episodes and the long-term risk of microvascular complications.

Expected indirect benefits

The study results may contribute to evaluating the impact of oral glucose-lowering medication on GV in Mexican patients with T2D who have significant glycemic dyscontrol.

General risk-benefit assessment of the proposed study

The oral glucose-lowering agents used in the study have potential risks such as hypoglycemia, gastrointestinal disorders, and increased frequency of urinary tract infections, which occur in only a small percentage of users, versus the benefit of controlling elevated glucose levels associated with micro and macrovascular complications.

Specify costs (direct/indirect, monetary, time participation, visits/travel) generated by the research for the study subjects

Patients must attend 8 visits, transportation costs will be covered by the study group.

Specify whether consultations, laboratory/imaging tests, and medical/surgical treatments generated due to the study will be covered by the patient/research subject or not

Expenses for emergencies or complications associated with the use of study medications will be covered by medical expense insurance.

Report who will cover the costs associated with the research

The study was designed by the principal investigator, without interference from the pharmaceutical industry. The project will receive financial support from AstraZeneca, which will provide dapagliflozin, consumables, and analysis costs, as well as publication fees. None of the research team members will receive financial compensation for their participation.

If applicable, specify the incentives offered (incentive is understood as an offer or influence that compels an action without implying a significant deviation from our general life plan; e.g., giving a book for participating)

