The guidelines of the American Association of Clinical Endocrinologists recommend the use of combination therapy with MET + another glucose lowering medication when HbA1c at diagnosis is >7.5 and $\leq 9\%$, and in patients with HbA1c $>9\%$ without classic symptoms of diabetes; dual or triple therapy can also be initiated [23]. In a study of 16 T2D patients, dapagliflozin 5 mg showed statistically significant improvement in body composition (fat mass) from week 8 [49]. In another study of 40 hypertensive patients treated with dapagliflozin vs hydrochlorothiazide, an impact on blood vessel vasodilation was found after 4 weeks of dapagliflozin treatment [50]. The effect of administration of dapagliflozin decreased glycemic excursions, reduced GV, and prevented atherosclerosis damage in preclinical studies [45]. In a case report of a patient with MODY, administration of gliclazide with dapagliflozin improved GV [46].

Henry et al. [37], using CGM, determined GV in patients with uncontrolled T2D (HbA1c 7.5% to 10.5%) who were previously treated with Metformin >1500 mg/day (50%) or insulin > 30 units/day (50%), to whom dapagliflozin or placebo was additionally administered. A decrease of 18.2 mg/dL in average glucose with CGM and a decrease of 15.3 mg/dL in MAGE were reported. Based on this study, the sample size calculation was performed.

9. Problem Definition

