Definition of Follow-up Variables

- **Primary Variable:** Change from baseline in GV (MAGE) in mg/dL after 12 weeks of treatment between the DAPA+ MET group versus the MET monotherapy group.
- **Secondary Variables:**
 - Change from baseline (absolute difference) in HbA1c levels (%) after 12 weeks of treatment between the DAPA + MET group versus the MET monotherapy group.
 - Change from baseline (total difference) in insulin levels (μ U/mL) after 12 weeks of treatment between the DAPA + MET group versus the MET monotherapy group.
 - Change from baseline (absolute difference) in oxidative stress measurement (total antioxidant capacity) after 12 weeks of treatment between the DAPA + MET group versus the MET monotherapy group.
 - Change from baseline (total difference) in the measurement of inflammation biomarkers (VCAM-1 and adiponectin) after 12 weeks of treatment between the DAPA + MET group versus the MET monotherapy group.
 - Change from baseline (absolute difference) in body fat quantification after 12 weeks of treatment between the DAPA + MET group versus the MET monotherapy group.
 - Change from baseline (total difference) in the parameters of cardio-metabolic risk factors (weight (kg), total cholesterol (mg/dL), HDL (mg/dL), LDLc (mg/dL), albuminuria (mg/mg creatinine), and blood pressure (mmHg)) after 12 weeks of treatment between the DAPA + MET group versus the MET monotherapy group.

Methods for Data Collection

Electronic Record containing the clinical history collected via telemedicine (Phone call/Videocall, Whatsapp, Teams, Zoom or Google Forms), information gathered at each visit, notes containing patient physical examinations, physical activity questionnaires answered via telemedicine (Phone call/Videocall, Whatsapp, Teams, Zoom or Google Forms), Nutrition notes collected via telemedicine (Phone call/Videocall, Whatsapp, Teams or Zoom), and laboratory results. Patients will only be identified by their initials, date of birth, and the internal protocol folio number.

Monitoring and Auditing Procedures During Study Development

Not applicable

Criteria for Failure and Success

- **Failure:** No decrease in GV in the DAPA + MET group compared to the MET monotherapy group.
- **Success:** A decrease in GV in the DAPA+ MET group compared to the MET monotherapy group.

Sample Size

The sample size was determined using the difference of means formula:

$$n = (Z\alpha / 2 + Z\beta)^2 * 2 * \sigma^2 / d^2,$$

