A reduction in glucose variability from 4.85 to 2.2 was estimated with an expected standard deviation of 2.8 in the MAGE index (values based on the study by R. R. Henry et al., "Effects of Dapagliflozin on 24-Hour Glycemic Control in Patients with Type 2 Diabetes: A Randomized Controlled Trial," *Diabetes Technol. Ther.*, vol. 20, no. 11, pp. 715–724, Nov. 2018.), with an alpha value of 0.05 and a power of 0.80, resulting in a sample size of 88 subjects, with 44 subjects in each treatment group. No adjustments were included in the sample size calculation to estimate the subjects required for the estimated differences in secondary variables.

Description of techniques, devices, and/or instruments to be used (Including special mechanical, electronic, cybernetic equipment)

Continuous glucose monitoring will be performed using the iPro™2 Continuous glucose monitor, from Medtronic®, to determine the MAGE value as follows:

- **Calculation of Mean Amplitude of Glucose Excursion (MAGE):**
 - In the first step, all local maximum/minimum values are determined.
 - The next step is an evaluation of maximum/minimum pairs against the standard deviation (SD).
 - If the difference from minimum to maximum is greater than the SD, this variation from the mean measurement is retained.
 - If the local maximum/minimum is less than 1 SD, it is excluded from further calculations.
 - These channels are retained and summed to achieve the MAGE
- Glycated hemoglobin (HbA1c) will be measured using HPLC (Variant II Turbo, Biorad).
- Insulin levels will be measured with Access-2 equipment (Beckman Coulter, Inc.).
- Oxidative stress will be measured with the BioAssay Systems antioxidant assay kit (DTAC-

100) (QuantiChrom Antioxidant Assay Kit) (BioAssay Systems).

- VCAM-1 will be measured using ELISA kits (Merck Millipore, USA).
- Adiponectin measured using ELISA kits (Merck Millipore, USA).
- Body fat quantification by bioelectrical impedance with the Jawon scale, model⁵ IOI 353 - JMW160.
- Anthropometric variables will be measured using standardized techniques; these include height, weight, waist, and hip circumferences.
- BMI will be calculated using the equation: weight / height² (kg/m²).
- Blood pressure will be measured considering the mean of two determinations after sitting for at least 5 minutes.
- Mean arterial pressure (MAP) will be calculated with the formula: (systolic blood pressure * 0.33) + (diastolic blood pressure * 0.66).

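### The sample-size effect (MAGE falling from 4.85 to 2.2, no unit) is credited to a study for which the protocol itself reports a 15.3 mg/dL fall; neither glucose unit reconciles the two, so the 80% power claim is unsupported for the reported effect

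*Protocol*

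**What the plan says.** The last paragraph of the protocol's Background describes a study that added dapagliflozin or placebo to metformin or insulin and measured glycaemic variability by CGM. Its results are given as: "A decrease of 18.2 mg/dL in average glucose with CGM and a decrease of 15.3 mg/dL in MAGE were reported". The next sentence reads: "Based on this study, the sample size calculation was performed".

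The Sample Size section of the protocol, citing the same study, gives different planning values: "A reduction in glucose variability from 4.85 to 2.2 was estimated with an expected standard deviation of 2.8 in the MAGE index". The SAMPLE SIZE paragraph under Methods and the opening paragraph of the SAP repeat these values with the same attribution. The protocol's Justification of sample size repeats them without naming a source. No unit is attached to 4.85, 2.2 or 2.8 in any of the four places.

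The calculation is stated "with an alpha value of 0.05 and a power of 0.80", giving 44 per arm and 88 in total. The protocol's Statistical Analysis section specifies two-tailed testing. The primary variable, in Definition of Follow-up Variables and again in Outcomes and Variables, does carry a unit: "Change from baseline in GV (MAGE) in mg/dL after 12 weeks of treatment", compared between the two arms.

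**The concern.** One study is given two MAGE effects, 15.3 mg/dL and 2.65 in an unstated unit, and the plan does not connect them. The formula used is the one for a difference between two group means, so its d must be a between-arm difference on the scale of the primary variable. If d has a different unit, is a different contrast or was mis-transcribed, the 80% power does not belong to the effect that the protocol reports from its source.

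This is the only power justification for the primary endpoint. The protocol's Criteria for Failure and Success count the absence of a decrease in glycaemic variability relative to metformin as failure. A non-significant result could then be taken as evidence of no effect, on the strength of a power figure that may not apply.

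**Working it through.** **Inputs**

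- Planning d = 4.85 − 2.2 = 2.65 and SD = 2.8, no unit (protocol Sample Size; SAP).
- Reported MAGE effect of the cited study: 15.3 mg/dL (protocol Background).
- Two-sided alpha 0.05, power 0.80, 1:1 allocation, 44 per arm (protocol).
- Conversion assumed: 1 mmol/L = 18 mg/dL.

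**1. The plan's own figure.** The formula is n per arm = 2 × SD² × (1.960 + 0.842)² / d². With the printed inputs, 2 × 2.8² × 7.849 / 2.65² = 17.5, so 18 per arm (19 by the t-test), not 44. That 44 does not follow from the inputs is a separate fault. It matters here because correcting only that arithmetic would show about 99% power at 44 per arm for d = 2.65, while leaving the origin of d unexplained.

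**2. Can a unit reconcile the two effects?**

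| Unit of 2.65 | In mg/dL | Ratio to 15.3 |
|---|---|---|
| mg/dL | 2.65 | 2.65 / 15.3 = 0.17 |
| mmol/L | 2.65 × 18 = 47.7 | 47.7 / 15.3 = 3.1 |

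A match would need 15.3 / 2.65 = 5.77 mg/dL per unit, which is neither glucose unit.

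**3. What 44 per arm delivers.** By the two-sample t-test, 44 per arm has 80% power for a between-arm difference of 0.604 SD. Taking 15.3 mg/dL as a between-arm difference (an assumption), the SD may be at most 15.3 / 0.604 = 25.3 mg/dL.

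**4. Power for 15.3 mg/dL at 44 per arm, over assumed SDs**

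| SD (mg/dL) | Power |
|---|---|
| 20 | 94% |
| 25 | 81% |
| 30 | 66% |
| 40 | 43% |
| 50 | 29% |

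**5. Where the planning SD falls.** The documents give "with an expected standard deviation of 2.8 in the MAGE index" and no unit.

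- Read as mmol/L, it is 2.8 × 18 = 50.4 mg/dL. Power is then 29% at 44/44 and 27% with the SAP's 41 and 39 completers. For 80% power, n = 2 × 50.4² × 7.849 / 15.3² = 170.3, so 171 per arm.
- Read as mg/dL, power for 15.3 mg/dL is about 100%. This reading is incoherent, because a value of 4.85 mg/dL cannot fall by 15.3 mg/dL.

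**The case against.** The strongest reply is that the two figures may not be the same quantity. The Background describes a placebo-controlled study and does not say whether 15.3 mg/dL is a within-arm change or is placebo-adjusted. The values 4.85 and 2.2 could be before and after in one arm, or values from two arms. Different contrasts from one study need not agree. This stands as a possibility, but it does not rescue the calculation: the documents do not say it, and a within-arm change would be the wrong d for a two-group formula.

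A second reply is that mg/dL is the only unit the protocol gives for MAGE, and that in mg/dL the power for 15.3 is about 100%. The incoherence of that reading makes mmol/L the more plausible unit, but this is inference, not something the documents state.

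A reader might therefore infer that the trial had only 29% power at its planning SD. The documents do not support that as a plain statement. It needs both SD 2.8 in mmol/L and 15.3 mg/dL as a between-arm difference, and neither is stated. A reader might also infer that 15.3 mg/dL is the effect the protocol expects and so the right planning value. The protocol reports it only as a background result; the effect it says it estimated is 4.85 to 2.2. Either figure may have been transcribed wrongly from a study that is not available here.

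Finally, the SAP shows 88 patients randomised and 80 completing, so restated power changes no enrolment, and a planning error does not bias the estimate. That is correct. It limits the consequence to the power claim and to how a non-significant result is read.

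**Conclusion.** The discrepancy holds on the documents alone. Two MAGE effects are credited to one study, they differ by a factor of about 6 if 2.65 is in mg/dL (15.3 / 2.65 = 5.8) or about 3 if it is in mmol/L, and nothing reconciles them. The stated 80% power is not supported for the effect that the protocol reports from its source.

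How far actual power falls short, if it does, cannot be fixed from the documents. If 15.3 mg/dL is a between-arm difference, the threshold is an SD of about 25 mg/dL for the analysed quantity, whatever the unit of 2.8. The 29% figure is conditional and should be cited only with its two assumptions. Which of the two effects is right is not decided here.

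**What to change.** In the protocol's SAMPLE SIZE paragraph under Methods, its Sample Size and Justification of sample size sections, and the first paragraph of the SAP:

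1. Give the unit, source and contrast type (within-arm or between-arm) of 4.85, 2.2, 2.8 and, from the Background, 15.3 mg/dL, and reconcile them against the cited study. Do not attribute 4.85 to 2.2 to that study unless this is confirmed.
2. Replace the 80% power statement with what 44 per arm delivers: 80% power for a between-arm difference of 0.60 SD. Add power for the reconciled effect, in mg/dL, over a range of SDs such as 20 to 50 mg/dL.
3. State that a non-significant MAGE result will be interpreted by its 95% CI against the reconciled effect, not as evidence of no effect.

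The cost is a check of the source and revised wording in both documents. The stated power may become less favourable. No extra patients are needed.
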